8 APPENDIX

8.1 APPENDIX 1. TABLE SHELLS

Table 5. Baseline characteristics (*example*)

	Apixaban (n=XX)	Warfarin (n=XX)
Age – mean, SD		
Gender		
Female		
Male		
Insurance type		
National Health Insurance		
Medical Aid		
CHA ₂ DS ₂ -VASc score		
Mean (SD)		
0-1		
2		
3		
4		
≥5		
HAS-BLED		
Mean (SD)		
0-2		
≥3		
Charlson Comorbidity Index		
Mean (SD)		
0-1		
2-3		
≥4		
Comorbidities		
Stroke/TIA		
Systemic embolism		
MI		
Bleeding*		
Hypertension		
Diabetes mellitus		
CAD		

	Apixaban (n=XX)	Warfarin (n=XX)
PAD		
Heart failure		
COPD		
Renal disease		
Medication use		
NSAIDs		
Antiplatelet		
PPI		
H2-receptor antagonist		
Digoxin		
Statin		
Antiarrhythmics		

*Bleeding will be identified as the same with the definition of major bleeding outcomes and the transfusion procedure codes (see Table 14 for codes).

Table 6. Hazard ratios for each comparison (*example*)

	Apixaban (n=XX)	Warfarin (n=XX)	Apixaban vs warfarin (n=XX)	P value
	Event rate	Event rate	HR (95% CI)	
Effectiveness endpoints				
Stroke/systemic embolism				
Safety endpoints				
Major bleeding				

APPENDIX 2. DATA DERIVATION DETAILS

Table 7. Effectiveness Outcomes Codes

Type	KCD Code or Procedure Code
Hemorrhagic stroke*	I60, I61, I62, I690, I691, I692
Ischemic stroke*	G459, I63, I693
Systemic embolism**	I74
*Brain CT/MRI	CT: HA441, HA451, HA461, HA471, HA851 MRI: HE101, HE102, HE135, HE201, HE202, HE235, HE301, HE302, HE401, HE402, HE501, HE502, HE535
**Any CT/MRI	CT: HA401, HA402, HA403, HA404, HA405, HA406, HA407, HA408, HA409, HA410, HA411, HA412, HA413, HA414, HA415, HA416, HA424, HA425, HA434, HA435, HA443, HA444, HA445, HA446, HA447, HA448, HA449, HA453, HA456, HA457, HA458, HA459, HA463, HA464, HA465, HA466, HA467, HA468, HA469, HA473, HA474, HA475, HA476, HA477, HA478, HA479, HA496, HA497, HA801, HA805, HA809, HA813, HA834, HA835, HA853, HA856, HA857, HA858, HA859, S4852 MRI: HE103, HE104, HE105, HE106, HE107, HE108, HE109, HE110, HE111, HE112, HE113, HE114, HE115, HE116, HE117, HE118, HE119, HE120, HE121, HE122, HE123, HE124, HE125, HE126, HE127, HE128, HE129, HE130, HE131, HE132, HE133, HE134, HE136, HE137, HE138, HE139, HE140, HE141, HE142, HE203, HE204, HE205, HE206, HE207, HE208, HE209, HE210, HE211, HE212, HE213, HE214, HE215, HE216, HE217, HE218, HE219, HE220, HE221, HE222, HE223, HE224, HE225, HE226, HE227, HE228, HE229, HE230, HE231, HE232, HE233, HE234, HE236, HE237, HE238, HE239, HE240, HE241, HE303, HE304, HE305, HE306, HE307, HE308, HE309, HE310, HE311, HE312, HE313, HE314, HE315, HE316, HE317, HE318, HE319, HE320, HE321, HE322, HE323, HE324, HE325, HE326, HE327, HE328, HE329, HE330, HE331, HE332, HE333, HE334, HE403, HE404, HE405, HE406, HE407, HE408, HE409, HE410, HE411, HE412, HE413, HE414, HE415, HE416, HE417, HE418,

NIS Protocol <X9001134>
Statistical Analysis Plan
<Version 3.0> <03 May 2018>

	HE419, HE420, HE421, HE422, HE423, HE424, HE425, HE426, HE427, HE428, HE429, HE430, HE431, HE432, HE433, HE434, HE503, HE504, HE505, HE506, HE507, HE508, HE509, HE510, HE511, HE512, HE513, HE514, HE515, HE516, HE517, HE518, HE519, HE520, HE521, HE522, HE523, HE524, HE525, HE526, HE527, HE528, HE529, HE530, HE531, HE532, HE533, HE534, HE536, HE537, HE538, HE539, HE540, HE541, HF101, HF102, HF104, HF105, HF106, HF107, HF201, HF202, HF305, HF306
--	--

*Brain CT/MRI will be used to define hemorrhagic stroke and ischemic stroke.

**Any CT/MRI will be used to define systemic embolism.

Table 8. Safety Outcomes Codes

Type	KCD Code or Procedure Code
Intracranial haemorrhage*	I60, I61, I62, I690, I691, I692, S064, S065, S066, S068
Gastrointestinal bleeding	I850, I983, K2211, K226, K228, K250, K252, K254, K256, K260, K262, K264, K266, K270, K272, K274, K276, K280, K282, K284, K286, K290, K3181, K5521, K625, K920, K921, K922
Other bleeding	D62, H448, H3572, H356, H313, H210, H113, H052, H470, H431, I312, N020-N029, N421, N831, N857, N920, N923, N930, N938, N939, M250, R233, R040, R041, R042, R048, R049, T792, T810, N950, R310, R311, R318, R58, T455, Y442, D683
*Brain CT/MRI	CT: HA441, HA451, HA461, HA471, HA851 MRI: HE101, HE102, HE135, HE201, HE202, HE235, HE301, HE302, HE401, HE402, HE501, HE502, HE535

*Brain CT/MRI will be used to define intracranial hemorrhage.

Table 9. CHA₂DS₂-VASc Score

Condition	KCD code	Point
Congestive heart failure	I50	1
Hypertension	I10-I15	1
Age	75+ years	2
Diabetes	E10-E14	1
Stroke	I63, I693 G459	2
Vascular disease	I21, I252, I70-I73	1
Age	65-74 years	1
Sex	Female	1

Table 10. HAS-BLED Score

Condition	KCD code	Point
Hypertension	I10-I15	1
Abnormal renal function	N183, N184	1
Abnormal liver function	B15-B19, C22, D684, I982, I983, K70-K77, Z944	1
Stroke	I63, I693, G459	1
Bleeding history or Predisposition*	Codes in Table 8	1
Labile INR	Not measurable	Not applicable
Elderly	65+ years	1
Drug therapy	Antiplatelets, NSAIDs	1
Alcoholism	E244, F10, G312, G621, G721, I426, K292, K70, K860, O354, P043, Q860, T510, X45, X65, Y15, Y90-Y91, Z502, Z714, Z721	1

* Blood transfusion will also be used to define other bleeding history (see Table 14 for blood transfusion codes).

Table 11. Charlson Comorbidity Index

Condition	KCD code	Point
Cerebrovascular disease	G45.x, G46.x, H34.0, I60.x-I69.x	1
Congestive heart failure	I09.9, I11.0, I13.0, I13.2, I25.5, I42.0, I42.5-I42.9, I43.x, I50.x, P29.0	1
Chronic pulmonary disease	I27.8, I27.9, J40.x-J47.x, J60.x-J67.x, J68.4, J70.1, J70.3	1
Dementia	F00.x-F03.x, F05.1, G30.x, G31.1	1
Diabetes without chronic complication	E10.0, E10.1, E10.6, E10.8, E10.9, E11.0, E11.1, E11.6, E11.8, E11.9, E12.0, E12.1, E12.6, E12.8, E12.9, E13.0, E13.1, E13.6, E13.8, E13.9, E14.0, E14.1, E14.6, E14.8, E14.9	1
Mild liver disease	B18.x, K70.0-K70.3, K70.9, K71.3-K71.5, K71.7, K73.x, K74.x, K76.0, K76.2-K76.4, K76.8, K76.9, Z94.4	1
Myocardial infection	I21.x, I22.x, I25.2	1
Peripheral vascular disease	I70.x, I71.x, I73.1, I73.8, I73.9, I77.1, I79.0, I79.2, K55.1, K55.8, K55.9, Z95.8, Z95.9	1
Peptic ulcer disease	K25.x-K28.x,	1
Rheumatologic disease	M05.x, M06.x, M32.x-M34.x M31.5M35.1, M35.3, M36.0	1
Diabetes with chronic complication	E10.2-E10.5, E10.7, E11.2-E11.5, E11.7, E12.2-E12.5, E12.7, E13.2-E13.5, E13.7, E14.2-E14.5, E14.7	2
Hemiplegia or paraplegia	G04.1, G11.4, G80.1, G80.2, G81.x, G82.x, G83.0-G83.4, G83.9	2
Any malignancy, including leukemia and lymphoma	C00.x-C26.x, C30.x-C34.x, C37.x-C41.x, C43.x, C45.x-C58.x, C60.x-C76.x, C81.x-C85.x, C88.x, C90.x-C97.x,	2
Renal disease	I12.0, I13.1, N03.2-N03.7, N05.2-N05.7, N18.x, N19.x, N25.0, Z49.0-Z49.2, Z94.0, Z99.2	2
Moderate or severe liver disease	I85.0, I85.9, I86.4, I98.2, K70.4, K71.1, K72.1, K72.9, K76.5, K76.6, K76.7	3
AIDS/HIV	B20.x-B22.x, B24.x	6
Metastatic solid tumor	C77.x-C80.x	6

Table 12. Baseline Medications

Class	Drug
NSAIDs	Bromfenac, Celecoxib, Diclofenac, Etodolac, Fenoprofen, Flurbiprofen, Ibuprofen, Indomethacin, Ketoprofen, Ketorolac, Naproxen, Meclofenamate, Mefenamic acid, Meloxicam, Nabumetone, Oxaprozin, Piroxicam, Sulindac, Tolmetin
Antiplatelets	Aspirin, Clopidogrel, Prasugrel, Ticlopidine, Cilostazol, Abciximab, Tirofiban, Dipyridamole, Ticagrelor
PPI	Omeprazole, Pantoprazole, Lansoprazole, Rabeprazole, Esomeprazole, Dexlansoprazole
H ₂ -receptor antagonists	Cimetidine, Ranitidine, Famotidine, Nizatidine, Roxatidine, Lafutidine
Antiarrhythmics	Quinidine, Procainamide, Mexiletine, Propafenone, Flecainide, Amiodarone, Bretylium, Dronedarone, Propranolol, Atenolol, Esmolol, Verapamil, Diltiazem, Sotalol
Digoxin	Digoxin
Statins	Atorvastatin, Fluvastatin, Lovastatin, Pitavastatin, Pravastatin, Roxuvastatin, Simvastatin

Table 13. Exclusion Criteria

Condition	KCD Code or Korean Procedure Codes
Valvular AF/ prosthetic heart valves	I05, I08, I09, I34, Q23, T820, T826, Z952, Z953, Z954 - Korean Procedure Codes: M6580, M6581, M6582, O1791, O1792, O1793, O1794, O1795, O1796, O1797, O1798, O1799, M6531, M6532, M6533, O1690, O1730, 1740, O1750, O1760, O1770, O1781, O1782, O1783, O1810, O1826
End-stage of chronic kidney disease/ dialysis/ kidney transplant	N185, T824, Y602, Y612, Y622, Y841, Z49, Z992, E1022, E1122, E1222, E1322, E1422, Z940
Venous thromboembolism	I636, I676, I801, I802, I803, I808, I809, I81, I822, I823, I829, I26
Thyrotoxicosis	E05
Pericarditis	I30, I31, I32
Hypertrophic	I422

NIS Protocol <X9001134>
Statistical Analysis Plan
<Version 3.0> <03 May 2018>

Condition	KCD Code or Korean Procedure Codes
cardiomyopathy	
Hip or knee replacement*	N0711, N0715, N1711, N1715, N1721, N1725, N2070, N2072, N2077, N2710, N2712, N2717, N3710, N3712, N3717, N3720, N3722, N3727, N4710, N4712, N4717, N4720, N4722, N4727
Elective defibrillation/ radiofrequency ablation/ left atrial appendage occlusion*	M5880, M6540, M6542, M6545, M6547, M6511

[*Note] Hip or knee replacement, elective defibrillation, radiofrequency ablation, and left atrial appendage occlusion will be identified using procedure codes.

Table 14. Blood Transfusion Codes

Condition	Korean procedure code
Whole Blood	X1001
Whole Blood	X1002
Fresh Liquid Plasma for Whole Blood 320ml	X2011
Fresh Liquid Plasma for Whole Blood 400ml	X2012
Packed RBC for Whole Blood 320ml	X2021
Packed RBC for Whole Blood 400ml	X2022
Washed RBC for Whole Blood 320ml	X2031
Washed RBC for Whole Blood 400ml	X2032
Fresh Frozen Plasma for Whole Blood 320ml	X2041
Fresh Frozen Plasma for Whole Blood 400ml	X2042
Frozen Plasma for Whole Blood 320ml	X2051
Frozen Plasma for Whole Blood 400ml	X2052
Cryoprecipitate for Whole Blood 320ml	X2061
Cryoprecipitate for Whole Blood 400ml	X2062
Platelet rich plasma for whole blood 320ml	X2071

NIS Protocol <X9001134>
Statistical Analysis Plan
<Version 3.0> <03 May 2018>

Condition	Korean procedure code
Platelet Rich Plasma for Whole Blood 400ml	X2072
Platelet Concentrate for Whole Blood 320ml	X2081
Platelet Concentrate for Whole Blood 400ml	X2082
Leukocyte Poor Packed RBC for Whole Blood 320ml	X2091
Leukocyte Poor Packed RBC for Whole Blood 400ml	X2092
Packed WBC for Whole Blood 320ml	X2101
Packed WBC for Whole Blood 400ml	X2102
Leukocyte Filtered Packed RBC for Whole Blood 320ml	X2111
Leukocyte Filtered Packed RBC for Whole Blood 400 ml	X2112
Leukocyte Filtered Packed Platelet Concentrate for Whole Blood 320ml	X2121
Leukocyte Filtered Packed Platelet Concentrate for Whole Blood 400ml	X2122
Red Blood Cells, Cryopreserved and Thawed for Whole blood 320ml	X2131
Red Blood Cells, Cryopreserved and Thawed for Whole blood 400ml	X2132
Plasma, Cryoprecipitate Reduced for Whole blood 320ml	X2141
Plasma, Cryoprecipitate Reduced for Whole blood 400ml	X2142
Fresh Blood	X3010

NIS Protocol <X9001134>
Statistical Analysis Plan
<Version 3.0> <03 May 2018>

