4.4 COVARIATES

Table 4. Baseline Variables

Variable	Role	Operational definition
Age	Baseline characteristic and potential confounder	Age at index date
Sex	Baseline characteristic and potential confounder	
 1. Male 2. Female
Types of health insurance	Baseline characteristic and potential confounder	
Types of health insurance divided as the following:
 
 1. National Health Insurance 2. Medical aid

NIS Protocol <X9001134>
 Statistical Analysis Plan
 <Version 3.0> <03 May 2018>

Variable	Role	Operational definition
CHA ₂ DS ₂ -VASC	Baseline characteristic and potential confounder	
CHA₂DS₂-VASC as continuous data or dichotomous data. The score will be calculated using the following KCD codes (Appendix 2, Table 9):
 
 1. Congestive heart failure 2. Hypertension 3. Diabetes mellitus 4. Stroke/TIA/TE 5. Vascular disease 6. Age ≥ 75 7. Age 65-74 8. Female
HAS-BLED	Baseline characteristic and potential confounder	
HAS-BLED as continuous data or dichotomous data. The score will be calculated using the following KCD codes (Appendix 2, Table 10):
 
 1. Hypertension 2. Abnormal renal function 3. Abnormal liver function 4. Stroke 5. Bleeding history or predisposition: refers to any bleeding codes 6. Age > 65 7. Antiplatelet or NSAID use 8. Alcoholism 
[Note] Labile international normalized ratio is not available in HIRA data and does not apply to patients on aspirin, or NOACs, so the modified HAS-BLED score has a maximum value of 8 instead of 9.

Charlson Comorbidity Index	Baseline characteristic and potential confounder	Charlson Comorbidity Index as continuous data or dichotomous data. The index will be calculated using the following KCD codes (Appendix 2, Table 11):

NIS Protocol <X9001134>
Statistical Analysis Plan
<Version 3.0> <03 May 2018>

Variable	Role	Operational definition
		
1. Myocardial infarction2. Congestive heart failure3. Peripheral vascular disease4. Cerebrovascular disease5. Dementia6. Chronic pulmonary disease7. Rheumatic disease8. Peptic ulcer disease9. Mild liver disease10. Diabetes without chronic complication11. Diabetes with chronic complication12. Hemiplegia or paraplegia13. Renal disease14. Any malignancy, including lymphoma and leukemia, except malignant neoplasm of skin15. Moderate or severe liver disease16. Metastatic solid tumor17. AIDS/HIV

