5 STATISTICAL METHODOLOGY AND STATISTICAL ANALYSES

5.1 STATISTICAL METHODS

Descriptive Analysis:

- All outcome variables will be summarized descriptively through the tabular and graphical display of mean values, medians, ranges, and standard deviations for continuous variables of interest and frequency distributions for categorical variables.
- The proportion of antithrombotics (aspirin, clopidogrel, aspirin and clopidogrel combination, warfarin, NOACs) at index date will be examined.
- Appropriate tests (e.g., t-test, chi-square test) will be used based on the distribution of the measure. The $p < 0.05$ considered significant.

Multivariate Analysis:

Propensity score method

The estimation of propensity score will be performed to control for confounders in each sub-dataset: (1) each NOAC versus NOAC; (2) each NOAC versus warfarin; (3) each NOAC versus aspirin.

Propensity scores are estimated by logistic regression analyses that incorporate potential treatment predictors as independent variables and types of index treatment as dependent variable (e.g., apixaban=1, warfarin=0). Covariates in the logistic regression model will

include variables such as age, sex, CCI score, CHA₂DS₂-VASc score, HAS-BLED score, and comorbidities, but the final list of these covariates will be discussed and determined after reviewing the results of descriptive analysis of the pre-matched datasets. Further, we will report the *c*-statistic of the propensity score that indicates the degree to which the propensity score model discriminates between treated patients and untreated patients.

After estimation of propensity score, we will perform propensity score matching (PSM). 1:1 matching without replacement will be performed.

The populations would be first matched using PSM according to their index treatment. For these matched populations we should then explore the proposed subgroups by: making an assessment of patient numbers in the subgroups and checking that patient characteristics are still similar between the index treatments in the subgroups. If they are similar, then conduct interaction term analysis is being conducted to determine whether the treatment effect varies between the subgroups. If the populations are no longer similar in characteristics, then re-matching via PSM will be performed for the subgroups.

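### SAP Table 9 gives no heart-failure point for I11.0, I13.0 or I13.2 and no vascular point for I22, although SAP Table 11 classes these codes as heart failure and MI

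*SAP*

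**What the plan says.** SAP section 4.4 (Table 4) builds CHA₂DS₂-VASc from one code table: "The score will be calculated using the following KCD codes (Appendix 2, Table 9". In that table the relevant rows are:

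- heart failure: "Congestive heart failure I50 1"
- hypertension: "Hypertension I10-I15 1"
- vascular disease: "I21, I252, I70-I73" (1 point)

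Table 11, for the Charlson index, has a row with the same congestive heart failure label and ten code groups: "I09.9, I11.0, I13.0, I13.2, I25.5, I42.0, I42.5-I42.9, I43.x, I50.x, P29.0". Its myocardial infarction row is "I21.x, I22.x, I25.2".

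The SAP gives no reason for the differences. Section 4.4 allows "CHA₂DS₂-VASC as continuous data or dichotomous data", with no cut-off stated for the dichotomy. Section 5.1 says the propensity model will "include variables such as age, sex, CCI score, CHA₂DS₂-VASc score, HAS-BLED score, and comorbidities". Section 3.2 lists the score as a possible subgroup variable, and secondary objective 2 (section 2.2) defines its low-risk population by a low score. The baseline shell (Table 5) bands the score as 0-1, 2, 3, 4 and 5 or more. It also has separate heart-failure and MI rows with no code list assigned to either.

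**The concern.** Three codes that the SAP itself calls congestive heart failure count only as hypertension in the stroke-risk score. One code that it calls myocardial infarction counts for nothing there. The same patient can thus have heart failure in one propensity covariate and not in another. Two programmers could also fill the heart-failure row of Table 5 differently, each following a list in the SAP.

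The Charlson score gives the propensity model some protection, because it carries the wider list. The uses that rest on CHA₂DS₂-VASc alone have no such second source: the score bands, any score subgroup, and the low-risk population of secondary objective 2. There, one point can decide where a patient is placed.

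**Working it through.** **Step 1. Where each code lands**

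| Code | Table 11 label | Table 9 row | Table 9 points |
|---|---|---|---|
| I11.0, I13.0, I13.2 | Congestive heart failure | Hypertension only | 1 |
| I50 | Congestive heart failure | Congestive heart failure | 1 |
| I21, I25.2 | Myocardial infarction | Vascular disease | 1 |
| I22 | Myocardial infarction | none | 0 |

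**Step 2. Score as written**

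Score = heart failure (1) + hypertension (1) + diabetes (1) + stroke (2) + vascular (1) + age (65-74: 1; 75 and over: 2) + female (1). The maximum is 9.

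**Step 3. Profiles, with no other scoring item present**

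| Patient | Table 9 as written | With I11.0, I13.0, I13.2 and I22 added |
|---|---|---|
| Man 60, I11.0 only | 0 + 1 = 1 | 1 + 1 = 2 |
| Woman 60, I11.0 only | 0 + 1 + 1 (sex) = 2 | 3 |
| Man 70, I11.0 only | 0 + 1 + 1 (age) = 2 | 3 |
| Woman 80, I11.0 only | 0 + 1 + 2 (age) + 1 (sex) = 4 | 5 |
| Man 60, I11.0 and I50 | 1 + 1 = 2 | 2 |
| Man 60, I22 only | 0 | 1 |
| Woman 60, I22 only | 0 + 1 (sex) = 1 | 2 |

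I13.0 and I13.2 give the same results as I11.0. The shift is exactly one point, and it vanishes once an I50 claim (or, for I22, another Table 9 vascular code) is present. The first and last patients move from band 0-1 to band 2 in Table 5. The man with I22 only stays in band 0-1.

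**Step 4. The rest of the Table 11 heart-failure list**

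- I25.5, I42.0, I42.5-I42.9 and I43 earn nothing in Table 9. A man of 60 with I42.0 only scores 0, against 1 if it counted as heart failure. However, I42.6 lies in this range and Table 10 uses it for alcoholism.
- I09.9 has no practical effect, because Table 13 excludes I09 and that exclusion covers the 12-month baseline.
- P29.0 is a perinatal-chapter code, in a cohort restricted to age 18 and over.

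**Step 5. How many patients (assumption)**

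The documents give no frequency. If 0.5% to 10% of the anticipated 150,000 were affected, that would be 0.005 × 150,000 = 750 to 0.10 × 150,000 = 15,000 patients, with a mean score shift of 0.005 to 0.10. The 150,000 is the figure before inclusion and exclusion criteria are applied.

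**Step 6. Effect on balance (assumption)**

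Change in standardized difference ≈ (difference between arms in affected share × 1 point) / SD of the score. With a share difference of 1 to 5 percentage points and an SD of 1.5 to 2, the range is 0.01/2 = 0.005 to 0.05/1.5 = 0.033. The SAP's imbalance threshold is 0.1.

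**The case against.** CHA₂DS₂-VASc and Charlson are different instruments, and section 4.4 assigns each its own table. Their lists differ elsewhere too: stroke against cerebrovascular disease, and renal and liver disease between Tables 10 and 11. The programmer's instruction for CHA₂DS₂-VASc is unambiguous, and an I50-only item may be deliberate. Part of this stands. Nothing in the documents makes Table 11 the reference definition for the other score, so importing its whole heart-failure list would be a preference. It does not explain why codes the SAP names as heart failure or MI should earn no such point in the score that defines a stated objective's population.

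Three stronger readings are tempting but unsupported:

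- **Every patient with one of these codes loses a point.** Only those without I50 do, or, for I22, those without another Table 9 vascular code.
- **The score can only be too low.** That is true of the rows compared here, but not of the whole table. Measured against Table 11, Table 9's vascular row is wider in places: it takes I72 and all of I73, while Table 11's peripheral vascular row has only I73.1, I73.8 and I73.9.
- **The main comparisons are materially biased.** Charlson is also a listed covariate, the final covariate list is still open, and the change in balance in Step 6 is below the SAP's threshold.

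The consequences are also conditional. Subgroup analyses are optional, the 0-1 band comes from an example shell, and no cut-off defines low risk. The documents therefore show that membership can change, not that it will for a known number of patients. The SAP's check of balance within subgroups, with re-matching if needed, protects the comparison there but does not correct who was placed in the subgroup.

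**Conclusion.** The point holds in a limited form. I11.0, I13.0 and I13.2 without I50, or I22 without another Table 9 vascular code, leave a patient exactly one point below what the SAP's own labels imply. This matters for score bands, score subgroups and the low-risk group of secondary objective 2. The shortfall is measured against the SAP's own classification, not an external standard. The number affected cannot be derived from the documents, and the 750 to 15,000 above only illustrates an assumed 0.5% to 10%. Bias in the primary hazard ratios is probably small, a judgement that rests on Charlson remaining in the propensity model and on the assumed range in Step 6. This is a cheap improvement, not a flaw in the primary comparison.

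**What to change.** 1. In SAP Table 9, add I11.0, I13.0 and I13.2 to the congestive heart failure row, keeping them in the hypertension row, and add I22 to the vascular disease row.
2. For the heart-failure row of Table 5, state I50, I11.0, I13.0 and I13.2 as the code set. For the MI row, state I21, I22 and I25.2.
3. Leave I25.5, I42.0, I42.5-I42.9 and I43 to a sensitivity analysis of the score. Do not copy I09.9 or P29.0.

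If the sponsor prefers I50 alone, the SAP should say why, and the wider set should be run as a sensitivity analysis.

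The cost is two edited derivation rows, two code lists for a table shell and one extra run of the score. The small downside is slightly less comparability with studies that use I50 only.

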### 8.2.2 Exclusion criteria

Patients meeting any of the following criteria will not be included in the study.

1. Medical claims indicating diagnosis or procedure for hip/knee replacement surgery within 6 weeks prior to index date
2. Medical claims indicating a diagnosis code indicative of rheumatic mitral valvular heart disease, mitral valve stenosis during the 12-month baseline period  
(Valvular AF / Prosthetic heart valves)
3. Medical claims indicating a diagnosis code of VTE (Venous thromboembolism) during the 12-month baseline period
4. Medical claims indicating a diagnosis or procedure code of transient AF, or cardiac surgery during the 12-month baseline period

(Thyrotoxicosis, Hypertrophic cardiomyopathy, Elective defibrillation, radiofrequency ablation, or left atrial appendage occlusion)

5. Medical claims indicating a diagnosis code of other conditions during the 12-month baseline period  
(End-stage chronic kidney disease / Kidney transplant / Dialysis / Pericarditis)
6. For the comparison of “NOAC versus NOAC”, and “NOAC versus warfarin”, patients with any OACs (apixaban, dabigatran, rivaroxaban, or warfarin) in the pre-index period (from 1 year prior to the day before index date)
  - *[NOTE] Patients prescribed antiplatelets in the pre-index period will not be excluded.*
7. For the comparison of “NOAC versus aspirin”, patients with following medications in the pre-index period (from 1 year prior to the day before index date)
  - NOAC user: OACs (apixaban, dabigatran, rivaroxaban, warfarin)
  - Aspirin user: none
  - *[NOTE] NOAC user is defined as OAC naïve user and aspirin user is allowed to have OACs or antiplatelets in the pre-index period.*

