Exclusion criteria	Exclusion criteria	HIRA database	
Claims with the following KCD codes or procedure codes:
 
 
1. Valvular AF/ Prosthetic heart valves: I05, I08, I09, I34, Q23, T820, T826, Z952, Z953, Z954            - Korean procedure codes: M6580, M6581, M6582, O1791, O1792, O1793, O1794, O1795, O1796, O1797, O1798, O1799, M6531, M6532, M6533, O1690, O1730, 1740, O1750, O1760, O1770, O1781, O1782, O1783, O1810, O1826
 
2. End-stage of chronic kidney disease/dialysis: N185, T824, Y602, Y612, Y622, Y841, Z49, Z992, E1022, E1122, E1222, E1322, E1422
 
3. Kidney transplant: Z940
 
4. Venous thromboembolism: I636, I676, I801, I802, I803, I808, I809, I81, I822, I823, I829, I26
 
5. Hip or knee replacement            - Korean procedure codes: N0711, N0715, N1711, N1715, N1721, N1725, N2070, N2072, N2077, N2710, N2712, N2717, N3710, N3712, N3717, N3720, N3722, N3727, N4710, N4712, N4717, N4720, N4722, N4727
 
6. Thyrotoxicosis: E05
 
7. Pericarditis: I30, I31, I32
 
8. Hypertrophic cardiomyopathy: I422
 
9. Elective defibrillation, radiofrequency ablation, or left atrial appendage occlusion            - Korean procedure codes: M5880, M6540, M6542, M6545, M6547, M6511
 

Follow-up period	Follow-up period	HIRA database	
From the index date until the first occurrence of the following whichever came first:
 
 
1. Discontinuation: maximum of a 30-day gap after the calculated time to finishing the pack based on pack size and number of tablets per day. Switching: switch to any other study drugs
 
2. Outcome occurrence
 
3. Study ends: November 30, 2016
 

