3 ANALYSIS SETS/ POPULATIONS

3.1 FULL ANALYSIS SET

Inclusion criteria

Patients must meet all of the following inclusion criteria to be eligible for inclusion in the study:

1. Patients aged 18 years or older on the index date
2. Patients had ≥ 1 medical claim for AF (refer to Table 1) before or on the index date with at least one hospitalization or at least two outpatient visits:

[Diagnosis codes for inclusion criteria]

KCD-6 ¹⁾	KCD-7 ²⁾
I48 (Atrial fibrillation and flutter)	I48 (Atrial fibrillation and flutter)
I480 (Atrial fibrillation)	I480 (Paroxysmal atrial fibrillation)
I481 (Atrial flutter)	I481 (Persistent atrial fibrillation)
	I482 (Chronic atrial fibrillation)
	I483 (Typical atrial flutter)
	I484 (Atypical atrial flutter)
	I489 (Atrial fibrillation and atrial flutter, unspecified)

KCD-6, Korean version of ICD-10 (6th revision); KCD-7, Korean version of ICD-10 (7th revision)

1) KCD-6 diagnosis codes will be used from 1 July 2015 to 31 December 2015.

2) KCD-7 diagnosis codes will be used from 1 January 2016 to 30 November 2016.

[NOTE] KCD code is based on ICD-10 and almost similar, but KCD code is slightly different from ICD-10 (e.g., ICD-10 is more subdivided and extensive than KCD code).

3. Patients prescribed aspirin, warfarin, or NOACs in intake period (from July 1, 2015 to November 30, 2016)
[Note] NOACs include apixaban, dabigatran and rivaroxaban.

Exclusion criteria

Patients meeting any of the following criteria will not be included in the study.

1. Medical claims indicating diagnosis or procedure for hip/knee replacement surgery within 6 weeks prior to index date
2. Medical claims indicating a diagnosis code indicative of rheumatic mitral valvular heart disease, mitral valve stenosis during the 12-month baseline period
(Valvular AF / Prosthetic heart valves)
3. Medical claims indicating a diagnosis code of VTE (Venous thromboembolism) during the 12-month baseline period
4. Medical claims indicating a diagnosis or procedure code of transient AF, or cardiac surgery during the 12-month baseline period
(Thyrotoxicosis, Hypertrophic cardiomyopathy, elective defibrillation, radiofrequency ablation, or left atrial appendage occlusion)
5. Medical claims indicating a diagnosis code of others during the 12-month baseline period
 - (End-stage chronic kidney disease / Kidney transplant / Dialysis / Pericarditis)

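### Procedure code 1740 in the valvular-AF exclusion list is malformed in both documents, and the sentence of exclusion 2 is narrower than the code row that carries it out

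*SAP*

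**What the plan says.** Protocol 8.2.2 and SAP 3.1 state exclusion 2 in the same words. In the SAP it reads "Medical claims indicating a diagnosis code indicative of rheumatic mitral valvular heart disease, mitral valve stenosis during the 12-month baseline period", followed in brackets by "Valvular AF / Prosthetic heart valves". Neither document defines valvular AF further.

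The operational list is in the exclusion-criteria entry of Protocol 8.3 and in the first row of SAP Table 13 (Appendix 2), under that same bracketed label. It has ten diagnosis codes, "I05, I08, I09, I34, Q23, T820, T826, Z952, Z953, Z954", and 26 procedure codes. The procedure codes include the run "O1690, O1730, 1740, O1750, O1760, O1770" in the SAP, and the Protocol prints the same string.

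A note under SAP Table 13 says "Hip or knee replacement, elective defibrillation, radiofrequency ablation, and left atrial appendage occlusion will be identified using procedure codes". The valvular row is not among them, although it carries procedure codes too.

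On the meaning of the diagnosis codes, the documents say only that "KCD code is based on ICD-10 and almost similar, but KCD code is slightly different from ICD-10". Neither gives a title for I34, Q23 or any of their sub-codes.

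**The concern.** This row decides who counts as nonvalvular, so it acts on all nine comparison sub-datasets in SAP 3.1. It is also the only code list for valvular atrial fibrillation, which SAP Table 3 names as an example of an event that may precede discontinuation or switching.

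Two things look wrong. First, a code without its leading letter will not be found by an exact or prefix match against procedure codes that start with a letter. Patients identifiable only through that procedure would be kept. Nothing would flag it: an unmatched string in a list raises no error, and the validation in Protocol 8.8 consists of log review and inspection of listings and summary tables.

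Second, someone who reads only the sentence of exclusion 2 would describe a different cohort from the one the codes select. The report could then state an NVAF definition that the data do not follow.

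**Working it through.** No sample-size, power or alpha figure is involved. The check is a format test on the procedure codes and a side-by-side reading of the criterion and its row.

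**Format test (one letter followed by four digits), all procedure codes in SAP Table 13**

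| Row | Codes | Conforming | Exception |
|---|---|---|---|
| Valvular AF / prosthetic valves | 26 | 25 | 1740 |
| Hip or knee replacement | 24 | 24 | none |
| Defibrillation, ablation, appendage occlusion | 6 | 6 | none |
| Total | 26 + 24 + 6 = 56 | 25 + 24 + 6 = 55 | 1 |

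The imaging codes in SAP Tables 7 and 8 and the transfusion codes in SAP Table 14 also all begin with a letter. The same defect stands in two separate documents, so a fault in reading the PDF is unlikely. The neighbours are O1730 and O1750, so the missing letter is probably O. That is an inference from position, because neither document contains the HIRA code list.

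**Sentence against row**

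| Aspect | Sentence of exclusion 2 | Bracketed heading and code row |
|---|---|---|
| Conditions | Rheumatic mitral disease; mitral stenosis | Valvular AF and prosthetic valves |
| Source of evidence | Diagnosis code | 10 diagnosis codes and 26 procedure codes |
| Level of coding | Not stated | 5 whole three-character categories (I05, I08, I09, I34, Q23) and 5 four-character codes |

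Three features of the documents show that these differences are of substance:

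- Exclusions 1 and 4 expressly allow either a diagnosis or a procedure. Exclusion 2 mentions a diagnosis code only.
- SAP Table 13 uses four-character codes where it wants a narrow set (I422, N185, I636). I34 and Q23 without a fourth character therefore read as the whole category.
- SAP Table 11 counts I09.9 towards congestive heart failure, while Table 13 excludes all of I09. On the SAP's own usage, part of the row is filed under something other than mitral valve disease.

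**Number of patients.** The only size given is about 150,000 (Protocol 8.5), before the inclusion and exclusion criteria are applied. The documents give no frequency for any valve diagnosis or procedure, so no count can be derived for either part of the point.

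**The case against.** The strongest reply is that the bracketed label is part of exclusion 2 and that the row carries the same label. On that reading the row does implement the criterion, and the Protocol's amendment log records that procedure codes were added under this heading. This stands. A reader might infer that the row fails to implement exclusion 2, but the documents do not support that. They show a sentence and a heading of different width, with valvular AF left undefined.

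A reader might also infer that eligible patients with non-rheumatic mitral regurgitation are wrongly removed, perhaps in large numbers, and that I34 and Q23 should be cut down to particular sub-codes. That does not follow either. No passage says such patients are to be kept. The code titles are not in the documents, which themselves warn that KCD and ICD-10 differ in detail. A broad valvular exclusion is also a legitimate choice for an NVAF cohort. Any count would rest on an assumed prevalence with no basis in the plan.

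On 1740, it can fairly be said that the other 25 procedure codes and the 10 diagnosis codes may catch most of the same patients, and that a search for the digits anywhere in the code would still find it. Both limit the likely effect. Neither makes the printed code correct.

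Finally, the exclusion uses baseline data and the same rule for every treatment group. A reader might still suspect that missed valve patients gather in one arm and distort a comparison. The documents neither say what the procedure is nor give its use by treatment, so that remains conjecture.

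**Conclusion.** The point holds in two limited parts.

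1. 1740 is malformed in both documents, the one exception among 56 procedure codes. As written it would probably match no claim, so patients whose only valve record in the 12-month baseline is that procedure would remain in the cohort. They are probably few. This assumes matching on the full code or its leading characters, and that HIRA procedure codes follow the format of the other 55.
2. The sentence of exclusion 2 is narrower than its bracketed heading and code row, both in the conditions covered and in the use of procedure codes. This rests on the documents alone and needs no outside code titles.

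The size cannot be derived for either part. The consequence is for who is included and how the NVAF population is described. No bias in any hazard ratio has been demonstrated.

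**What to change.** - Look up 1740 in the HIRA procedure code list and correct it, probably to O1740, in Protocol 8.3 and SAP Table 13.
- Reconcile the sentence of exclusion 2 with its row in Protocol 8.2.2 and SAP 3.1. Either reword the sentence to state the scope the codes select, including the whole categories and the procedures, or change the row to match the sentence. The sponsor should choose the scope and record it.
- Extend the note under SAP Table 13 to say that the valvular row uses both diagnosis and procedure codes.
- Report how many patients exclusion 2 removes, by code group, so that readers can see what the definition does.

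The cost is one code lookup, one string in two tables, and a sentence in each document. It is cheapest before the cohort is built. Protocol section 5 plans the start of data collection for 01 Feb 2018, before the current version of 03 May 2018. If selection has already been run, that step would have to be repeated.
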